5.2.6.2 Definition of evaluable patient

For decisions on dose escalation, an evaluable patient is defined as a patient who has received first cycle of combination treatment of BI 836880 and ezabenlimab and has been observed 3 weeks for first cycle except patients discontinue in the first cycle due to DLT. Patients who discontinue during the first treatment cycle for reasons other than a DLT will be non-evaluable for the determination of the MTD.

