A safety monitoring committee (SMC) meeting will be held to decide if the 2nd patient can be enrolled to the study. Subsequent enrollment at all dose levels within dose escalation, each patient in a given cohort (dose level) will be observed for a minimum of 48 hours after first BI 836880 and ezabenlimab application for acute reaction monitoring before allowing treatment for subsequent patient in the same cohort. As described in [Section 6.1](#) of the protocol, during the treatment phase, after administration of BI 836880 and ezabenlimab, patients are required to be hospitalized under close surveillance with access to intensive care for at least 48 hours after administration of trial medication to allow close monitoring for infusion-related reactions or other adverse events and availability of patients for PK visits. The sponsor will contact the investigator to verify if any acute reaction was investigated before allowing treatment for subsequent patient in the same cohort. For any dose-escalation cohort, at least 2 patients will be required. After all patients in a cohort have either experienced a DLT or have been observed for at least one cycle (1 cycle is defined as 3 weeks) without a DLT, the BLRM will be updated with the newly accumulated data. The overdose risk will then be calculated for each dose, and escalation will be permitted to all doses which fulfil the EWOC criterion and dose escalation rules according to [Section 4.1.3](#). Decision on further recruitment (dose escalation, de-escalation or cohort expansion) will be made by a Safety Monitoring Committee (SMC) based on the collected safety data as well as other data (e.g. PK/PD data) when available.

If DLTs are observed in the first 2 consecutive patients of a previously untested dose level, subsequent enrolment to that cohort will be stopped. The BLRM will be re-run to confirm

that the dose-level still fulfils the EWOC criterion. Decision will be made whether the next patients will be enrolled on the same dose level, or if they will be enrolled to a lower dose level.

Part 2:

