on the time of occurrence and the severity of the reaction, the investigator may consider administering additional supportive medication, e.g. corticosteroids for re-introduction. Infusion rate and premedication for further treatment cycles should be adapted according to Investigator decision, but adaption of administration scheme need to be agreed with sponsor. If an infusion related reaction is Grade 3 or higher in severity at any point during the study, treatment with ezabenlimab has to be permanently discontinued.

Premedication:

No premedication will be required for BI 836880 IV or ezabenlimab infusion. If a patient expressed sign of infusion reaction at any BI 836880 treatment, a premedication will be considered for all subsequent treatment infusions (dosage and schedule according investigator's decision) comparable to following scheme:

- Acetaminophen/Paracetamol 650 mg - 1000 mg p.o., or equivalent
- Antihistamine p.o. or i.v., equivalent to Diphenhydramine 50 mg i.v.

Drug re-administration criteria after the first cycle has been completed for Part 1:

Before initiating a new treatment cycle the actual health status will be assessed according to [Flow Chart](#) and described in [Section 5.2.5](#). To continue treatment with further cycles, all of the following criteria must be met:

- No uncontrolled hypertension (according to Exclusion-Criterion #9)
- QTcF <=480 ms (according to Exclusion-Criterion #8)
- Acceptable tolerability (in case of an adverse event at the planned start of a treatment cycle patients may continue therapy only after recovery to a level which would allow further therapy; i.e. CTCAE grade 1 or pre-treatment value or considered not clinically significant)

In case one of the above mentioned criteria is not fulfilled the patient should be re-evaluated for up to 2 weeks. Any case of a delay in treatment cycle should be communicated to the Clinical Monitor at Boehringer Ingelheim. The investigator in agreement with the Clinical Monitor will decide about further treatment of individual patient, based on known risk/benefit of BI 836880 and ezabenlimab.

Rescreening is generally not allowed. In individual cases, rescreening can be considered in alliance with the sponsor.

In case of a DLT (drug related AEs CTCAE Grade 3, 4 according to [Table 5.2.6.1: 1](#)), the patient will discontinue treatment.

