Once a DLT has recovered to CTCAE grade 1 or pre-treatment values, the study drugs may be re-started at a lower dose level in case the patients benefit from the study drug after discussion between investigator and Clinical Monitor at Boehringer Ingelheim.

Drug re-administration criteria after the first cycle has been completed in Part 2:

Before initiating a new treatment cycle the current health status of the patient will be assessed according to the [Flow Chart](#).

To continue treatment with further cycles, all of the following criteria must be met:

1. Pre-infusion SBP should be < 160 mmHg and pre-infusion DBP should be < 100 mmHg; study drug administration of both study drugs should be temporarily delayed until BP < 160/100. Please see [Table 10.2.1: 1](#) in [Appendix 10.2.1](#), which describes the guidelines for BP management and study drug administration.
2. QTcF <=480 ms (according to Exclusion-Criterion #8)
3. Echocardiography if clinically indicated (based on investigators judgment) with Left Ventricular Ejection Fraction (LVEF) $\geq 50\%$
4. Acceptable tolerability (in case of an adverse event at the planned start of a treatment cycle patients may continue therapy only after recovery to a level which would allow further therapy in the opinion of investigator).

In case the above mentioned criteria 2, 3, and 4 are not fulfilled, the patient should be re-evaluated as needed. Any case of a delay in treatment cycle should be communicated to the Clinical Monitor at Boehringer Ingelheim. The investigator in agreement with the Clinical Monitor will decide about further treatment of individual patient, based on known risk/benefit of BI 836880 and ezabenlimab.

Dose reduction guidelines

Part 1:

Administration of trial drugs has to be stopped temporarily in case of a DLT (see [Section 5.2.6.1](#)). Patients may continue therapy only after recovery from DLT to at least fulfil retreatment criteria. The future dose of BI 836880 must be a tested dose which is one dose level below the dose received by the patient (Table 4.1.4: 1 and [4.1.4: 2](#) below) Treatment has to be discontinued in case the DLT is not reversible.

Table 4.1.4: 1 Dose reduction recommendations for BI 836880 in Part I

BI 836880 received dose	BI 836880 reduced dose
720 mg	500 mg
500 mg	360 mg
360 mg	Stop BI 836880

In case of AEs (DLTs) that can be definitely characterized as ezabenlimab related, dose can be reduced.

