Since a Bayesian approach is applied, prior distributions f for each of the parameter vectors $\theta_1 = (\log(\alpha_1), \log(\beta_1))$, $\theta_2 = (\log(\alpha_2), \log(\beta_2))$ and for the interaction term η need to be specified. The prior distributions for θ_1 and θ_2 will be specified as mixtures of two multivariate normal distributions, i.e.

$$a(\theta_k) = a_{1,k} f_1(\theta_k) + a_{2,k} f_2(\theta_k)$$

with

$a_{1,k}, a_{2,k}$ the prior mixture weights, $k=1,2$ and

$$f_i(\theta_k) = \text{MVN}(\mu_{ik}, \Sigma_{ik}) \quad (k=1,2),$$

the multivariate normal distribution of the i -th component with mean vector μ_{ik} and covariance matrix Σ_{ik} , where

$$\Sigma_{ik} = \begin{pmatrix} \sigma_{ik,11}^2 & \sigma_{ik,11}\sigma_{ik,22}\rho_{ik} \\ \sigma_{ik,11}\sigma_{ik,22}\rho_{ik} & \sigma_{ik,22}^2 \end{pmatrix}$$

Mixture prior distributions have the advantage that they allow for specification of different logistic dose-toxicity curves, therefore making the prior more robust.

A weakly informative normal prior distribution will be used for η .

The estimated probability $\pi_{12,d1,d2}$ of a DLT at each dose combination d_1, d_2 from the model will be summarized using the following intervals:

Under dosing: [0.00, 0.16)

Targeted toxicity: [0.16, 0.33)

Over dosing: [0.33, 1.00]

The BLRM-recommended dose combination for the next cohort is the level with the highest posterior probability of the DLT rate falling in the target interval [0.16, 0.33) among the dose combinations fulfilling the EWOC principle. Per EWOC it should be unlikely (i.e., <25% posterior probability) that the DLT rate at the dose combination will exceed 0.33. However, the maximum allowable dose increment for the subsequent cohort will be no more than 100% for each compound.

The MTD may be considered reached if one of the following criteria is fulfilled:

1. The posterior probability of the true DLT rate in the target interval [0.16, 0.33) of the MTD is above 50%, OR
2. At least 8 patients have been treated in the study, of which at least 6 at the MTD.

Prior derivation:

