7.3 PLANNED ANALYSES

No per protocol set will be used in the analysis. However, important protocol deviations will be summarized. The TSAP will specify the important protocol deviations in detail.

For the determination of the MTD, only MTD-evaluable patients will be considered. For the analysis of secondary and [REDACTED] in Part 1, all patients in the treated set (i.e., patients treated with at least one dose of trial medication) will be included in the analysis. All analyses planned in Part 2 will be based on the treated set.

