7.3.1 Primary endpoint analyses

7.3.1.1 Primary endpoint analyses for Part 1

In order to identify the MTD(s) and the recommended dose(s) for Part 2 of the trial, the number of patients with DLTs at each dose combination during the Part 1 MTD evaluation period (the first cycle of the BI 836880 plus ezabenlimab combination) must be presented by descriptive statistics. Patients who discontinue during the first treatment cycle for reasons other than a DLT will be excluded from the determination of the MTD. In addition, the number of patients with DLTs that occurred during the entire treatment period will be summarized at each dose level. The BLRM will be rerun to re-evaluate the MTD and RP2D together with all relevant data collected during Part 2.

7.3.1.2 Primary endpoint analyses for Part 2

The primary endpoint for Part 2 of the trial is OR defined by confirmed CR or PR according to RECIST 1.1 for all cohorts except GBM as assessed by the Investigator. OR in GBM cohort will be evaluated using RANO criteria. Overall response will be analyzed in terms of the shrinkage estimator of the OR rate (ORR) based on BHM.

Note on primary endpoint analysis in cohort F:

In addition, OR from stage I and stage II will be analyzed separately using a Bayesian approach with meta-analytic predictive (MAP) prior after completion of stage II. Please refer to [Section 7.1.2](#) for more details on the derivation of the MAP prior and the final decision criterion. A naïve estimate (observed objective response rate) along with 95% CI (Clopper-Pearson) will also be provided.

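### MTD evaluability depends on the recorded reason for leaving cycle 1, so a patient with a cycle 1 DLT who leaves early for another recorded reason is excluded

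*Protocol*

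**What the plan says.** Section 5.2.6.2 defines the evaluable patient in two sentences. The first requires that the patient received the first cycle of the combination and "has been observed 3 weeks for first cycle except patients discontinue in the first cycle due to DLT". The second adds: "Patients who discontinue during the first treatment cycle for reasons other than a DLT will be non-evaluable for the determination of the MTD".

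Section 7.3.1.1 repeats the exclusion as an analysis rule: "Patients who discontinue during the first treatment cycle for reasons other than a DLT will be excluded from the determination of the MTD". Section 7.3 makes it binding: "For the determination of the MTD, only MTD-evaluable patients will be considered".

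Three other places bear on the point:

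- Section 2.1.2 sets the Part 1 primary endpoint as the number of patients with DLTs in the first cycle. It does not mention the reason for leaving.
- Section 3.1 times the model update by outcome: "After all patients in a cohort have either experienced a DLT or have been observed for at least one cycle" without a DLT.
- Section 4.1.4 describes treatment after a Part 1 DLT in two ways. Under the re-administration criteria, "the patient will discontinue treatment". Under the dose reduction guidelines, "Administration of trial drugs has to be stopped temporarily in case of a DLT".

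**The concern.** Whether a DLT was observed and why a patient stopped treatment are different facts, and the MTD data should depend on the first. Under the wording of 5.2.6.2 and 7.3.1.1, a patient with a DLT on day 8 who leaves on day 14 with progression recorded has not been observed for 3 weeks and did not discontinue because of the DLT. That patient fails both sentences of 5.2.6.2, and no other clause brings the patient back.

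The loss goes in one direction. It removes an event together with its patient, so the estimated DLT rate can only fall, and the escalation with overdose control (EWOC) criterion is then checked against data that look safer than they were. The rule also fits poorly with section 5.2.6.1, which adds late immune-related DLTs from after cycle 1 to the model: a DLT outside the window can count while one inside it is lost.

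A second, smaller problem lies within 5.2.6.2. A patient taken off treatment on day 18 for progression but followed to day 21 is evaluable under the first sentence and non-evaluable under the second.

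**Working it through.** **Step 1: the definitions applied to four patients.** All received the cycle 1 infusions.

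| Patient | 5.2.6.2, first sentence | 5.2.6.2, second sentence, and 7.3.1.1 | Counted by 2.1.2 as a cycle 1 DLT |
|---|---|---|---|
| DLT, stays under observation for 3 weeks | evaluable | not excluded | yes |
| DLT, leaves early, DLT is the recorded reason | evaluable | not excluded | yes |
| DLT, leaves early, another reason recorded | not evaluable | excluded | yes |
| No DLT, stops early for another reason, observed for 3 weeks | evaluable | excluded | no DLT to count |

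The third row is the anti-conservative exclusion. The fourth is the internal contradiction.

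**Step 2: reproduce the protocol's model figures.** The model is that of section 7.1.1.1, with reference doses 720 mg and 240 mg:

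- logit(π₁) = log α₁ + β₁ log(d₁/720), and logit(π₂) = log α₂ + β₂ log(d₂/240)
- π⁰ = π₁ + π₂ − π₁π₂
- odds(π₁₂) = odds(π⁰) · exp(η · d₁/720 · d₂/240)

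Priors are those of Table 7.1.1.1: 3. Three million prior draws were weighted by the binomial likelihood. P(overdose) is the posterior probability that π₁₂ is at least 0.33, and the limit is: "Per EWOC it should be unlikely (i.e., <25% posterior probability) that the DLT rate at the dose combination will exceed 0.33".

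| Scenario in Table 10.6.1: 1 | Dose (BI 836880/ezabenlimab, mg) | Protocol | Reproduced |
|---|---|---|---|
| 1A: 0/2 at 360/240 | 360/240 | 0.075 | 0.076 |
| 1A | 500/240 | 0.110 | 0.113 |
| 1A | 720/240 | 0.210 | 0.210 |
| 1B: 1/3 at 360/240 | 360/240 | 0.226 | 0.223 |
| 2D: 0/2 at 360/240, 2/6 at 500/240 | 500/240 | 0.188 | 0.184 |

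The agreement is within simulation error.

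**Step 3: remove one patient with a DLT.** The last column gives P(overdose) with the patient counted, then dropped.

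| Data: counted, then dropped | Dose checked | P(overdose) |
|---|---|---|
| 1/3, then 0/2 at 360/240 | 500/240 | 0.295 (blocked), then 0.113 (allowed) |
| 2/6, then 1/5 at 500/240, after 0/2 at 360/240 | 720/240 | 0.353 (blocked), then 0.194 (allowed) |
| 3/6, then 2/5 at 720/240, after 0/2 and 0/3 at the lower doses | 720/240 | 0.37 (blocked), then 0.22 (allowed) |
| 2/6, then 1/5 at 720/240, after 0/2 and 0/3 at the lower doses | 720/240 | 0.17 (allowed), then 0.075 (allowed) |

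The first row is the protocol's own pair of Scenarios 1B and 1A, which differ by exactly one patient with a DLT. The protocol's table keeps the dose at 360/240 in 1B and allows both 500/240 and 720/240 in 1A. Two patients also still meet the section 3.1 minimum for a cohort. In the second row, with the patient dropped, 720/240 has a target-interval probability of 0.435 against 0.385 at 500/240. The step from 500 to 720 is (720 − 500)/500 = 44%, within the 100% cap, so the model would recommend it. In the last row nothing changes.

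**Step 4: remove one fully observed patient without a DLT.** Going from 1/3 to 1/2 at 360/240 raises P(overdose) at that dose from 0.223 to 0.320. This error is conservative, the opposite direction to step 3.

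**The case against.** The strongest reply is that the affected patient will be rare. One part of section 4.1.4 has a patient with a DLT discontinue treatment, so the DLT would usually be the recorded reason, and a patient with a DLT who stays for 3 weeks is evaluable anyway. This stands, and it makes the case narrow. It does not remove it: the dose reduction text in the same section requires only a temporary stop, and section 3.3.4.1 requires withdrawal only when the DLT has not recovered within 2 weeks. A patient can therefore have a DLT, remain in the trial and then leave for something else.

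There are also safeguards. Part 1 DLTs are reported as events of special interest (5.2.6.1), and the safety monitoring committee decides on all available safety data (5.2.6.3), so it would see a DLT that the model did not. Escalation is finished: the committee has chosen the Part 2 doses (4.1.2.2), and recruitment stopped in December 2021. This also stands. The escalation examples show how sensitive the model is; they are not decisions still to come.

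Four stronger readings are tempting, and the documents do not support them:

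- A reader might infer that a fully observed patient is simply dropped. The first sentence of 5.2.6.2 makes that patient evaluable, so this is a contradiction to settle, and dropping the patient would err on the cautious side.
- A reader might infer that section 3.1 already defines the MTD data by outcome. It sets when the model is updated, not who is analysed. It shows the intention, but it does not override 5.2.6.2.
- A reader might infer that any lost DLT changes the dose decision. The last row of step 3 shows otherwise.
- A reader might put a probability on the loss. The documents give no rate of early exit under another recorded reason, and exit is unlikely to be independent of the DLT, so no frequency can be defended.

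**Conclusion.** The point holds as a wording error with a known direction. As written, 5.2.6.2 and 7.3.1.1 exclude a patient whose DLT was observed in cycle 1 if that patient leaves before 3 weeks for another recorded reason. This contradicts the primary endpoint and can only lower the estimated toxicity. Near the EWOC limit one such patient moves P(overdose) across 0.25 (0.35 to 0.19 at 720/240 in the 2/6 against 1/5 case); further from the limit the conclusion is unchanged.

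These figures rest on the prior in Table 7.1.1.1: 3, which section 7.1.1.1 describes as illustrative and to be replaced by actual data. They show sensitivity and do not estimate what happened. The protocol does not show that any such patient exists, so nothing here implies that the selected dose is wrong. What remains affected is the reported Part 1 primary endpoint and the model rerun announced in section 7.3.1.1. Both need a single definition of the evaluable set.

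**What to change.** Replace the evaluability rule in 5.2.6.2, and the matching exclusion in 7.3.1.1, with one based on outcome. A patient who received the cycle 1 infusions is MTD-evaluable if a DLT occurred in the MTD evaluation period, whatever the reason for leaving, or if the patient was observed for the full 3 weeks. Only patients without a DLT whose observation ended early are non-evaluable. This restores the lost DLT, settles the contradiction within 5.2.6.2 and agrees with the timing rule in section 3.1.

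Apply the definition to the final Part 1 endpoint table and to the model rerun, and state whether any patient's status changes.

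The two statements in section 4.1.4 on treatment after a Part 1 DLT should also be reconciled with each other and with 3.3.4.1, because they affect which reason is recorded. Which of them is right is a clinical matter and is not addressed here.

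The evaluability change costs a sentence or two in each of two sections and needs no new data. The evaluable number and the DLT count may rise slightly.

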5.2.6.3 Maximum Tolerated Dose (MTD) and Recommended Phase II dose (RP2D)

The MTD may be considered reached if the probability that the true DLT rate is in target interval (16% - 33%) is sufficiently large. For detailed definition see statistical part ([Section 7.1](#)). The SMC may recommend stopping the dose finding phase after the criterion for MTD is fulfilled. Further patients may be included to confirm the MTD. If next dose level is recommended by the statistical model; however, the efficacy is considered sufficient at current dose level, the SMC may decide to include additional number of patients at this dose level, declare this dose as RP2D and no further dose escalation will happen.

Decision on next steps (dose escalation, de-escalation or cohort expansion) will be made by a SMC based on all available safety data, including DLT information from last cohort as described above but also findings from subsequent cycles as well as other data (e.g. PK/PD data) when available.

All SMC decisions of dose escalation, and to open a new cohort for recruitment will be communicated to the Investigators. Once MTD and RP2D are defined this information will be sent to authorities according to local regulations.

5.2.7 Assessment of adverse events

5.2.7.1 Definitions of AEs

Adverse event

An adverse event (AE) is defined as any untoward medical occurrence in a patient or clinical investigation subject administered a medicinal product and which does not necessarily have to have a causal relationship with this treatment.

An AE can therefore be any unfavorable and unintended sign (including an abnormal laboratory finding), symptom, or disease temporally associated with the use of a medicinal product, whether or not considered related to the medicinal product.

Serious adverse event

A serious adverse event (SAE) is defined as any AE which fulfils at least one of the following criteria:

- results in death,
- is life-threatening, which refers to an event in which the patient was at risk of death at the time of the event; it does not refer to an event that hypothetically might have caused death if more severe.
- requires inpatient hospitalization or
- requires prolongation of existing hospitalization,
- results in persistent or significant disability or incapacity, or is a congenital anomaly / birth defect,
or
- is deemed serious for any other reason if it is an important medical event when based on appropriate medical judgement which may jeopardize the patient and may require medical or surgical intervention to prevent one of the other outcomes listed in the above definitions.
- Examples of such events are intensive treatment in an emergency room or at home for allergic bronchospasm, blood dyscrasias or convulsions that do not result in hospitalization or development of dependency or abuse.

For Japan only: the following events will be handled as “deemed serious for any other reason”. AEs which possibly lead to disability will be reported as SAEs.

AEs considered “Always Serious”

Every new occurrence of cancer of new histology must be classified as a serious event regardless of the duration between discontinuation of the trial medication and must be reported as described in [Section 5.2.7.2](#), subsections **AE Collection** and **AE reporting to sponsor and timelines**”.

In accordance with the European Medicines Agency initiative on Important Medical Events, Boehringer Ingelheim has set up a list of further AEs, which by their nature, can always be considered to be “serious” even though they may not have met the criteria of an SAE as defined above.

The latest list of “Always Serious AEs” can be found in the eDC system. These events should always be reported as SAEs as described above.

Adverse events of special interest (AESIs)

The term AESI relates to any specific AE that has been identified at the project level as being of particular concern for prospective safety monitoring and safety assessment within this trial, e.g. the potential for AEs based on knowledge from other compounds in the same class. AESIs need to be reported to the sponsor’s Pharmacovigilance Department within the same timeframe that applies to SAEs, please see above.

The following are considered as AESIs:

Dose Limiting Toxicities

All DLTs are considered to be AESIs, and must be reported as such. The definition of DLT is presented in [Section 5.2.6.1](#). DLTs are no longer applicable in Part 2 of the study, therefore are no longer AESIs in Part 2.

Persistent hypertension despite treatment

A hypertensive episode will be considered an AESI if:

- SBP \geq 140 mmHg or DBP \geq 90 mmHg which persists longer than 2 days despite either the initiation of antihypertensive agent(s) in a patient without prior history of hypertension, or the intensification / addition of new antihypertensive agents in a patient with prior history of hypertension.

Immune-related adverse events (irAE)

Although all irAEs are to be reported as AEs, only clinically important irAEs need to be reported as AESIs as defined by the sponsor in [Appendix 10.3](#). Non-clinically important irAEs, such as mild to moderate rash and hypothyroidism, for example, do not need to be reported as AESIs. If an Investigator determines that a severe irAE or other clinically significant irAE that is not included in [Appendix 10.3](#) is medically significant, the investigator may also report this irAE as an AESI.

Recommendations for the management of irAEs are presented in [Appendix 10.4](#).

Infusion-related reactions

All infusion-related reactions need to be reported as AESIs.

In the event of an infusion-related reaction \leq Grade 2, the infusion rate of BI 836880 or ezabenlimab may be decreased by 50% or interrupted until resolution of the event and re-initiated at 50% of the initial rate until completion of the infusion. In patients experiencing infusion related reactions \leq Grade 2, subsequent infusions may be administered at 50% of the initial rate.

If a patient experiences an infusion-related reaction, acetaminophen and/or an antihistamine (e.g., diphenhydramine) and/or corticosteroid or equivalent medication per institutional standard may be administered prior to subsequent infusions at the discretion of the Investigator for secondary prophylaxis of infusion-related reactions. If an infusion-related reaction is Grade 3 or higher in severity at any point during the study, treatment with BI 836880 or ezabenlimab will be permanently discontinued.

As with any mAb, allergic reactions to BI 836880 and ezabenlimab administration are possible. Appropriate drugs and medical equipment to treat acute anaphylactic reactions must be immediately available, and trial personnel must be trained to recognize and treat anaphylaxis. The trial site must have immediate access to emergency resuscitation teams and equipment in addition to the ability to admit patients to an intensive care unit if necessary.

The following events describe those events that are to be considered potential infusion-related AEs. Regardless of grade, these events are considered as AESIs and must be reported within 24 hours of the event:

- Allergic reaction
- Anaphylaxis
- Cytokine-release syndrome
- Serum sickness
- Infusion reactions
- Infusion-like reactions

If the Investigator determines that another event (not on the list) may be a potential infusion related AE, the Investigator must report that event as an AESI.

Potential DILI

A potential DILI is defined by the following alterations of hepatic laboratory

- Parameters:
 - **For patients with normal aminotransferase levels at baseline:** an elevation of AST and/or ALT ≥ 3 fold ULN combined with an elevation of total bilirubin ≥ 2 fold ULN measured in the same blood draw sample and without evidence of cholestasis, OR aminotransferase elevations ≥ 10 fold ULN
 - **For patients with abnormal aminotransaminase levels at baseline >1 and <2.5 x ULN at baseline:** An elevation of AST and/or ALT ≥ 3 fold the baseline value combined with an elevation of bilirubin ≥ 2 fold ULN and the baseline value in the same blood sample; OR Aminotransferase elevations ≥ 5 fold the baseline value.
 - **For patients with abnormal aminotransaminase levels at baseline ≥ 2.5 and ≤ 5 x ULN at baseline (patients with liver metastases only):** An elevation of AST and/or ALT ≥ 2 fold the baseline value combined with an elevation of bilirubin ≥ 2 fold ULN and the baseline value in the same blood sample; OR Aminotransferase elevations ≥ 3 fold the baseline value.

These lab findings constitute a potential DILI alert and the patients experiencing these lab abnormalities need to be followed up according to the “DILI checklist” provided in the ISF, unless an underlying other than study drug(s) cause has been determined.

In case of clinical symptoms of potential DILI (icterus, unexplained encephalopathy, unexplained coagulopathy, right upper quadrant abdominal pain, etc.) without lab results (ALT, AST, total bilirubin) available, the investigator should make sure these parameters are analyzed, if necessary in an unscheduled blood test. Should the results meet the criteria of a potential DILI alert, the procedures described in the DILI checklist should be followed.

Severity of AEs

The severity of adverse events should be classified and recorded in the CRF according to the Common Terminology Criteria for Adverse Events (CTCAE).

Causal relationship of AEs

Medical judgement should be used to determine the relationship, considering all relevant factors, including pattern of reaction, temporal relationship, de-challenge or re-challenge, confounding factors such as concomitant medication, concomitant diseases and relevant history.

Arguments that may suggest that there is a reasonable possibility of a causal relationship could be:

- The event is consistent with the known pharmacology of the drug.
- The event is known to be caused by or attributed to the drug class.
- A plausible time to onset of the event relative to the time of drug exposure.
- Evidence that the event is reproducible when the drug is re-introduced
- No medically sound alternative aetiologies that could explain the event (e.g. pre-existing or concomitant diseases, or co-medications).
- The event is typically drug-related and infrequent in the general population not exposed to drugs (e.g. Stevens-Johnson syndrome).
- An indication of dose-response (i.e. greater effect size if the dose is increased, smaller effect size if dose is diminished).

Arguments that may suggest that there is no reasonable possibility of a causal relationship could be:

- No plausible time to onset of the event relative to the time of drug exposure is evident (e.g. pre-treatment cases, diagnosis of cancer or chronic disease within days / weeks of drug administration; an allergic reaction weeks after discontinuation of the drug concerned)
- Continuation of the event despite the withdrawal of the medication, taking into account the pharmacological properties of the compound (e.g. after 5 half-lives).
- Of note, this criterion may not be applicable to events whose time course is prolonged despite removing the original trigger.
- Additional arguments amongst those stated before, like alternative explanation (e.g. situations where other drugs or underlying diseases appear to provide a more likely explanation for the observed event than the drug concerned).
- Disappearance of the event even though the trial drug treatment continues or remains unchanged

